### Specific objectives

- To describe the improvement in gait ability in patients undergoing hip surgery after a functional recovery programme compared to the historical control group (exposed cohort).
- To describe the clinical and functional characteristics of the patients operated on for hip fracture in the SJD hospital in León who are being followed up by the new system of care implemented in comparison with the historical control group (exposed cohort).
- To analyse risk and protective factors related to the level of dependency and mortality at 30 days and one year of follow-up in patients operated on for hip fracture at the SJD hospital in León.
- To describe the impact of a functional recovery programme on the prevention and treatment of sarcopenia in the new unexposed cohort.
- To describe the quality of life and patient-reported outcomes in the new unexposed cohort.
- To analyse the impact of a functional recovery programme on the prevention of falls in elderly patients who have undergone hip fracture surgery.

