#### **Variables**

In the two groups that form part of this study, different variables specified in the database adapted from the National Hip Registry and the *International Fragility Fracture Network*, of which the HSJD is a member, will be collected.

Until now, data collection and patient follow-up was completed after one month and the data was transferred annually to the National Hip Fracture Register. In the new model proposed by orthogeriatrics unit of the HSJD, patients will be followed up in person at one and a half months, four months and one year, and at discharge, one month after discharge, three months, six months and one year, by means of a digital application.

The variables to be collected are described below:

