- Level 2: non-functional ambulation. Walking with great physical assistance from a person, and/or walking is only possible within a therapy session at home, or in hospital, between parallel bars
- Level 3: ambulation in the home, walking with light physical contact with a person. Is able to walk only indoors, on flat, horizontal surfaces, usually within a defined area.
- Level 4: walks autonomously in the home or neighbourhood environment, but needs supervision by a person. They can walk on uneven surfaces and can climb an occasional step.
- Level 5: independent community walking. Can walk on uneven terrain, up and down steps, ramps, kerbs, etc. Can walk considerable distances, but with obvious limp.
- Level 6: walks normally both indoors and outdoors, in the absence of a limp or other abnormality.

This scale is administered at admission, 6 weeks, 4 months and 1 year.

**Second group: the variables collected in this second section form part of the new model of care established by the orthogeriatric service, whereby the hip fracture patient will be followed up for up to one year after the intervention, therefore, they are variables that can only be measured in the cohort of unexposed patients.**

Patient follow-up variables (Table II):

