**Table II (continuation): Patient follow-up variables**

Variables	Unit of measurement	Type
Functional Capacity and Pain (Oxford Hip Score)	Points (0 to 48)	Quantitative and Qualitative
Falls Risk (STRATIFY Scale)	Points (0 to 5)	Quantitative and Qualitative
Medical complications	0= Fall. 1= Pneumonia. 2= New fractures. 3= Dementia. 4= Acute Myocardial Infarction 5= Pulmonary embolism. 6=Deep vein thrombosis; 7=Death.	Qualitative
Quality of life analysis: questionnaire EQ-5D-5L	Levels (1 to 3125) Points (0 to 100)	Qualitative Quantitative
Abbreviations: RNFC: National Hip Fracture Registry, mFAC: Modified Functional Ambulatory Classificator,		

- **Level of dependency: the Spanish version of the *Barthel Index* will be used (Annex I).** The "*Barthel Index*" provides quantitative information on the level of dependence for activities of daily living by measuring ten activities that are considered basic (441,42). This scale has been used in other studies and shows a direct relationship between high levels of dependency and poor physical health (441). "The Barthel Index has demonstrated good inter-observer reliability, with Kappa indices between 0.47 and 1.00, intra-observer reliability with a Kappa index between 0.84 and 0.97 and internal consistency with a Cronbach's alpha of 0.86-0.92 (39-41).

Test results:

- Values: 0-20 total dependency.
- Values: 21-60 severe dependence.

- Values: 61-90 moderate dependence.
- Values: 91-99 low dependency
- Values: 100 independence.

This scale is administered at 6 weeks, 4 months and 1 year.

- **Sarcopenia assessment: using the SARC-F scale (ANNEX II) (42).**

It is an easily accessible questionnaire, validated in Spanish, which allows the identification of subjects at risk of sarcopenia. The maximum score is 10 points. A score of < 4 points after the test indicates an acceptable state of health, while any score higher than this indicates a risk of sarcopenia (43).

This scale is administered at 6 weeks, 4 months and 1 year.

- **Assessment of functional capacity and specific hip pain: "Oxford Hip Score (OHS)" (ANNEX III)**

It has high repeatability and reliability, with a Cronbach's Alpha value of 0.84 preoperatively, ICC=0.94, and 0.89 at six months and one year (44).

It is a 12-item questionnaire, each item is answered on a five-level Likert-type scale where 4 is the minimum impact and 0 the most unfavourable (45).

Results:

0-19: Severe impact.

20-29: Moderate to severe impact.

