30-39: Mild to moderate impact.

40-48: Satisfactory condition.

This scale is administered at 1, 3, 6 and 12 months.

- **Monitoring of adverse events.**

During the follow-up period, information will be collected on variables derived from post-surgical and medical complications, and falls risk monitoring will be performed.

- **Adverse events. Catalogued in:**

0= Fall.

- 1= Pneumonia.
- 2= New fractures.
- 3= Dementia.
- 4= Acute Myocardial Infarction.
- 5= Pulmonary embolism.
- 6=Deep vein thrombosis.
- 7= Death.

This scale is administered at 6 weeks, 4 months and 1 year.

- **Falls risk scale: STRATIFY scale.**

It can predict which patients are at high risk of falls, with sensitivity values of 92% and specificity of 68% for the elderly population (46).

The total score of the STRATIFY scale is obtained based on the sum of the answers to the five questions, which can take values between zero and five. A score of 0 corresponds to a risk considered low, equal to 1 corresponds to a moderate risk and, finally, greater than or equal to 2 corresponds to a high risk (47).

Question:

1. Patient hospitalised for falls or with episodes of falls during hospitalisation?
2. Restless patient?
3. Are you a patient with visual impairment that affects your daily activity?
4. Patient with a frequent need to use the toilet?
5. Does the patient have a transfer or mobility score of 3 or 4?

However, in the last question, the score is obtained by combining two answers from the modified Barthel index in relation to, respectively, the patient's ability to:

- Transferring from bed to a chair
  - 0: incapable.
  - 1: needs significant assistance.
  - 2: Needs minimal assistance.

3: Independent.

- Level of mobility of the patient:

0: Immobile.

1: Independent with the help of a wheelchair.

2: Use walking aids or walk with the help of a person.

3: Independent.

This scale is administered at 6 weeks, 4 months and 1 year.

- **Quality of life analysis: EQ-5D-5L questionnaire (ANNEX IV) (48).**

It is a self-administered questionnaire divided into two parts, the descriptive system and the Visual Analogue Scale (VAS).

- The descriptive system EQ-5D-5L. describes health status along five dimensions:
  - Mobility.
  - Self-care.
  - Daily activities.
  - Pain/discomfort.
  - Anxiety/depression.

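### The objective on preventing falls has no comparator: fall events and STRATIFY are planned only in the 2021 programme cohort, so falls can be described there but no programme effect on them can be estimated

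*Combined protocol and SAP*

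**What the plan says.** The labels run against intuition. Under Study design, the 2021 patients who receive the programme are the non-exposed cohort and the 2020 historical controls are the exposed cohort.

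There are six specific objectives. Those on gait and on clinical characteristics name the historical control group. Those on sarcopenia and quality of life are confined to the 2021 cohort. The last one, "To analyse the impact of a functional recovery programme on the prevention of falls in elderly patients who have undergone hip fracture surgery", names neither a comparator nor a single cohort.

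Under Variables, the first group is collected in both cohorts. The second group, in Table II and its continuation, comes with the new care model, and the introductory paragraph says "they are variables that can only be measured in the cohort of unexposed patients". That table contains STRATIFY and the medical complications list, which starts "0= Fall. 1= Pneumonia. 2= New fractures". For both, the text states: "This scale is administered at 6 weeks, 4 months and 1 year".

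On the earlier system of care, the Variables section says: "Until now, data collection and patient follow-up was completed after one month".

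**The concern.** An impact on prevention is a difference between what happened with the programme and what would have happened without it. To estimate it, the study needs falls in patients without the programme or, much more weakly, falls in the same patients before it. If neither is collected in usable form, the study can report only how often 2021 patients fell.

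The risk lies in interpretation. With the objective worded as it stands, a report that follows it could attribute an uncontrolled fall frequency to the programme. Nothing in the analysis text would prevent this: the tests named under Analysis of results are for baseline characteristics, and no falls analysis is described.

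**Working it through.** The protocol gives no fall rate, effect size or precision for falls, so there is no planned figure to reproduce. The check traces each falls-related measurement to its cohort and time points.

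**1. Variables shared with 2020.** Table I lists age, sex, caregiver, Pfeiffer test, RNFC mobility, mFAC and side of fracture. None concerns falls. The 2020 data come from existing registry records.

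**2. Falls-related measurements and where they are planned.**

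| Measurement | 2020 cohort | 2021 cohort |
|---|---|---|
| Fall events (complications code 0) | none planned | 6 weeks, 4 months, 1 year |
| STRATIFY | none planned | 6 weeks, 4 months, 1 year |
| SARC-F item on falls in the past year (Annex II) | none planned | 6 weeks, 4 months, 1 year |

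Table III agrees: it lists no admission time for any of the three. The app questionnaires at 1, 3, 6 and 12 months are the Oxford Hip Score and EQ-5D-5L, not falls.

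**3. Between-cohort contrast.** The 2020 column is empty, so neither a difference nor a ratio can be formed. A larger sample does not help, because the missing quantity is a whole arm's outcome. Follow-up under the earlier system also ended at one month, before the first 2021 recording point, and the 4-month and 1-year points have no counterpart.

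**4. Contrast within 2021.** The programme has been standard practice since January 2021, so no concurrent group without it is planned. The Work plan starts the programme the day after the fracture and continues it after discharge for a total of 16 weeks. The first record of fall events and STRATIFY, at 6 weeks, is therefore made after it has begun. STRATIFY is in any case a risk score, not a count of falls.

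**5. The SARC-F item.** It asks about falls in the past year. Assume that recall runs back 12 months from the visit and that visits are counted from discharge, as the Sampling section says:

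- 6-week visit (1.5 months): 12 − 1.5 = 10.5 months before discharge, plus 1.5 months after it.
- 4-month visit: 12 − 4 = 8 months before discharge, plus 4 months after it.
- 1-year visit: 12 − 12 = 0 months before discharge; the window is the year after it.

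A crude before-after comparison of the 6-week and 1-year answers is thus possible. It is not a valid one. The two windows share the first 1.5 months after discharge. The early window covers the fracture itself and can include the fall that caused it, which would tend to make later answers look better whatever the treatment. The item has three ordered categories, not a count.

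**6. The descriptive count.** For the 2021 cohort only, the eligibility section makes the occurrence of complications a reason for withdrawal, while Table II codes a fall as a medical complication. Read together, a patient who falls could be withdrawn, so even a descriptive fall frequency could be truncated.

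**The case against.** Several arguments limit the point.

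- **Both years are said to be followed for a year.** The Study design section does say so. It names no falls variable, however, and the specific statements under Variables point the other way.
- **Table II is not strictly exclusive to 2021.** RNFC mobility and mFAC appear in both groups of variables. That overlap does not extend to fall events or STRATIFY.
- **A reader might infer that no before-after information on falls exists at all.** The documents do not support that, because the SARC-F item gives a crude contrast. What stands is that this contrast cannot carry a claim about prevention.
- **A reader might infer that the sarcopenia objective has the same defect.** It reads "To describe the impact of a functional recovery programme on the prevention and treatment of sarcopenia in the new unexposed cohort": it sets out to describe, and it names one cohort. The words for impact and prevention should not be taken there as an effect claim, but this is a minor matter of wording.
- **A reader might want a numerical size.** Letting the 2020 fall risk be anything from 0 to 1 gives a range 100 percentage points wide for any binary outcome with an unobserved comparator. That says nothing particular about this study.
- **The stakes are bounded.** Falls are the last of six specific objectives, the overall objective and hypothesis concern functional status, and no falls test is planned. The limitations section acknowledges the absence of randomisation, though not the missing falls comparator. A purely descriptive report would do no harm, but the objective as worded asks for more than that.

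**Conclusion.** The point holds for the falls objective. With the data as planned, the programme's effect on falls cannot be estimated between cohorts, and the one within-patient source is unsuitable for a claim about prevention. The size is qualitative: no falls measurements are planned for 2020, against three recording times in 2021. The conclusion rests on reading the second-group statement as applying to fall events and STRATIFY, and on there being no unlisted falls item in the 2020 records that the study intends to use. The point does not reach the overall objective, and falls in 2021 can still be described once the withdrawal rule is reconciled. It merits correction before analysis because it changes what the study may conclude.

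**What to change.** 1. Reword the last specific objective along these lines: describe the frequency of falls and the STRATIFY risk category during follow-up in the 2021 cohort. State that no programme effect on falls will be tested or claimed.
2. If the sponsor wishes to keep an effect objective, first establish whether 2020 falls can be obtained from existing records, ascertained in the same way and over the same window as in 2021. If they can, specify an adjusted comparison and its expected precision.
3. Reconcile the withdrawal criterion on complications with the coding of a fall as a medical complication. However that is settled, falls in patients who are then withdrawn should remain in the count.
4. State that the SARC-F past-year item will not be used as a before-after measure of the programme's effect on falls.
5. As a minor edit, make clear that the sarcopenia objective is descriptive and that its wording on impact and prevention claims no effect.

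Items 1, 4 and 5 cost only wording. Item 3 needs a decision on the withdrawal rule and its recording. Item 2 is optional and would mean a search of records. The downside is one fewer effect claim, which the design could not support.

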### Hypothesis

A multimodal functional recovery programme of therapeutic exercise with patient follow-up after hip fracture surgery in older people can achieve better results than standard practice (standardised nursing care plan) in terms of recovery of functional status prior to hip fracture.

## METHODOLOGY

### Study design

Longitudinal analytical observational study of ambispective cohorts with two groups, an exposed cohort (retrospective) and a non-exposed cohort (protective factor), made up of people over 65 years of age referred from the Emergency Department of the University Care Centre of León (CAULE) to the Hospital San Juan de Dios de León (HSJD) with a confirmed diagnosis of hip fracture and who underwent hip fracture surgery in the latter during the years 2020 and 2021, and who will be followed up during the year after surgery, in the latter, to undergo hip fracture surgery during the years 2020 and 2021 and who will be followed up during the year following the surgery.

Two groups:

- Non-exposed cohort (protective factor): group of patients operated on during the year 2021 in HSJD for hip fracture and to which the new programme implementing functional recovery and therapeutic exercise will be applied with follow-up for one year. The implementation of a functional recovery plan and subsequent follow-up is considered a protective factor in relation to the loss of functionality.
- Exposed cohort (retrospective): complete cohort of patients operated on during the year 2020 in HSJD for hip fracture and to whom no specific functional recovery plan was applied.

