### **Eligibility criteria for the unexposed cohort (protective factor).**

Inclusion criteria:

- Patients referred from the Emergency Department of the Complejo Asistencial de León (CAULE), with confirmation of the medical diagnosis of hip fracture by means of anterior-posterior and lateral radiography.
- Be over 65 years of age.
- Ability to walk before the fracture with or without the aid of instruments or people.
- Have signed the informed consent to participate in the research project.
- With access to a smartphone mobile phone with the option of installing applications.

Exclusion criteria:

- Polytrauma patients will be excluded.
- Metastatic origin of the fracture.
- Periprosthetic fracture.
- Patients with cognitive impairment that makes it impossible for them to use the PPP and who are not accompanied by a responsible person during the recovery process.

Withdrawal criteria:

- Mortality at hospital discharge.
- Presentation of complications.
- Non-compliance with the therapeutic plan or assessment process.

**Eligibility criteria** for the exposed (retrospective) cohort.

Inclusion criteria:

- Patients referred from the Emergency Department of the Complejo Asistencial de León (CAULE), with confirmation of the medical diagnosis of hip fracture by means of antero-posterior and lateral radiography.
- Be over 65 years of age.
- Ability to walk before the fracture with or without the aid of instruments or people.

Exclusion criteria:

- Polytrauma patients will be excluded.
- Metastatic origin of the fracture
- Periprosthetic fracture.

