## Sampling

**Sample and procedure for inclusion of patients in the unexposed cohort.**

In order to carry out an analysis of the new care model (functional recovery programme and patient follow-up through a digital application), the entire simple universe will be included, a complete cohort analysis, with follow-up at 1, 3, 6 and 12 months using a digital toolFollow-up will be carried out at 6 weeks, 4 months and 12 after discharge according to the protocol of the orthogeriatrics unit.

The patient will be given instructions on how to download the application to their mobile device. The application is available in the open repository of mobile applications for public use. Once the app is installed, the patient will be provided with a personal access code that does not include recognisable personal data. This code will be used to connect to the therapeutic plan and to the questionnaires provided by the patient when registering with the Traumatology Service. Only the principal investigator (PI) will have a system of correlation between the code and the patient's personal data, be responsible for its safekeeping.

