**Table III. Summary of variables, assessment instruments and collection period**

Variable	Questionnaire	Time of administration
March Capacity	RNFC scale	Entry, at 6 weeks, 4 months and 1 year.
	The walking capacity assessment scale (mFAC).	Entry, at 6 weeks, 4 months and 1 year.
Physical capacity	Barthel Index	At 6 weeks, 4 months and 1 year.
	Oxford Hip Score Scale	At the 1st, 3rd, 6th and 12th month.
Sarcopenia	SARC-F Scale	At 6 weeks, 4 months and 1 year.
Adverse Events	STRATIFY scale	At 6 weeks, 4 months and 1 year.
	Medical complications (ad hoc questionnaires)	At 6 weeks, 4 months and 1 year.
Quality of life	Questionnaire EQ-5D-5L	At the 1st, 3rd, 6th and 12th month.

- The functional recovery programme designed and implemented as standard practice from 1 January 2021. This programme consists of a series of presentations and videos, in simple language with information and recommendations. It will provide answers to patients' most frequently asked questions and will also allow patients to receive reminders regarding their care (recommended exercises, precautions to take in certain circumstances, alerts, etc.).

It is the clinician and the patient, or family member if applicable, who enters the data directly into the application, prior to accepting the legal clauses to that effect.

The study variables collected in the project are included among the clinical variables included in the orthogeriatric protocol for the care of hip fracture patients at the HSJD. In order to analyse those established for this study, the variables will be extracted from the data collection platform, the PI being responsible for the storage and processing of the data in accordance with current legislation.

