This programme is divided into 5 phases, each of these phases coincides with a level of the gait assessment scale. Each individual will start at the level assigned by the doctor and will only have access to the videos of the indicated level and the levels below it. As the patient meets the recovery goals, the physician will provide access to the higher level videos. The functional recovery plan begins the day after the hip fracture and continues after the patient has been discharged for a total of 16 weeks.

- The therapeutic plan for the historical control group (standard practice until 31 December 2020) consisting of postural changes described in the standardised nursing care plan. Within this plan, the patient was moved to a sitting position prematurely (within the first 24 hours) and started to ambulate within the following 48

hours, provided that the patient's general condition allowed it. This group did not receive any specific functional recovery plan.

- The patient is discharged from hospital and will be assigned a link where he/she will be able to access the online platform to send information from the questionnaires sent during the established periods of 1, 3, 6 and 12 months and will also be sent videos illustrating the rehabilitation exercises that he/she will have to perform during this period. The patient and/or carer will be explained how the tool works, how to access the digital information content and how to access the questionnaires. A means of contact will be provided to resolve doubts, if any. The PI will have access through the web/app platform to a control panel where he/she will be able to detect a patient's lack of adherence, if any, or alerts related to clinical evolution, allowing for exhaustive monitoring of the patient.
- Analysis of results: The data collected will be analysed with the SPSS programme. The mean, median and standard deviation of each of the variables will be calculated. Based on the data obtained from the existing literature(31), having selected a sample of 67 patients, a normal distribution can be assumed for all variables  
For baseline demographic and clinical characteristics, a comparison of means for quantitative variables (t-Student), and of proportions (Chi-square) for qualitative will be performed  
The statistical analysis will be carried out with a confidence level of 95%, so that statistically significant values will be considered to be those whose probability is < 0.05.

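### Non-compliance can withdraw 2021 patients only, yet no listed variable records what each patient received, and the rule conflicts with the promised whole-cohort analysis

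*Combined protocol and SAP*

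**What the plan says.** Study design describes the programme cohort as the "group of patients operated on during the year 2021 in HSJD for hip fracture", "to which the new programme implementing functional recovery and therapeutic exercise will be applied with follow-up for one year". The eligibility section adds signed consent and access to a smartphone. The comparator is the "complete cohort of patients operated on during the year 2020 in HSJD for hip fracture", who had no specific recovery plan.

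The programme lasts 16 weeks in all, begins in hospital and continues after discharge through app videos. Under Description of the process: "Each individual will start at the level assigned by the doctor and will only have access to the videos of the indicated level" and those below it. The physician opens higher levels as recovery targets are reached. The same section gives the principal investigator a "control panel where he/she will be able to detect a patient's lack of adherence".

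Withdrawal criteria appear for the 2021 cohort only. One is "Non-compliance with the therapeutic plan or assessment process". The 2020 cohort has inclusion and exclusion criteria but no withdrawal criteria. For the 2021 cohort, the Sampling section says "the entire simple universe will be included, a complete cohort analysis".

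Table III, "Summary of variables, assessment instruments and collection period", covers gait, physical capacity, sarcopenia, adverse events and quality of life. The text after it says that the variables set for this study will be extracted from the platform.

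**The concern.** The hypothesis concerns what the programme achieves, but the dataset as listed records only that a patient belonged to the cohort meant to receive it. Starting level, dates of level changes and use of the exercises are absent from Tables I to III.

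That would be a modest gap if nothing depended on compliance, but the withdrawal rule does. It acts on a quantity with no definition, time window or stored value, and it acts in one cohort. It also joins two different failures, not following the exercise plan and not attending assessments, so even a record of withdrawal would not show which occurred. Nobody could later establish who met the criterion.

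At stake are the direction of a possible bias in the main comparison and the reading of a small or null difference.

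**Working it through.** The plan states no figure on this point. Its only design figure, a sample of 67, is justified by an assumption of normality and involves no uptake or effect size. The check is therefore a reading of the documents followed by two short illustrations.

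**1. Is receipt recorded anywhere?**
- Table I: age, sex, caregiver, Pfeiffer score, pre-fracture RNFC mobility and mFAC, side of fracture. Nothing on treatment.
- Table II: RNFC mobility, mFAC, Barthel, SARC-F, Oxford Hip Score, STRATIFY, complications, EQ-5D-5L. Nothing on treatment.
- Table III: the follow-up instruments with their timing. Nothing on treatment.
- Could mFAC stand in for programme level? The text ties the five phases to the gait scale, but mFAC is described with seven levels (0 to 6), and it measures ability, not exercise done.
- Control panel: it can reveal lack of adherence, but no metric, cut-off, storage or export is described.
- Ethical aspects, Confidentiality: collection is limited to what the study strictly needs, and data are destroyed at the end. A measure not named in the protocol may be impossible to recover later.

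**2. Do the rules agree?** The Sampling section analyses the whole 2021 cohort. The eligibility section withdraws non-compliers from that cohort. No sentence says whether withdrawal means leaving the analysis, so both cases need to be followed through.

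**3. If withdrawn patients leave the analysis.** Let u be the proportion who comply and E the programme's effect in compliers. Let S be the advantage in recovery that compliers would have had over non-compliers without any programme. Assume the 2020 cohort has the same mix of patients and is analysed whole.
- Expected 2020 recovery: p0 = u·b_c + (1 − u)·b_n, where b_c − b_n = S.
- 2021 compliers only: b_c + E.
- Difference: b_c + E − p0 = E + (1 − u)·S.

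The excess over E is (1 − u)·S: 0.2·S, 0.4·S and 0.6·S at 80%, 60% and 40% compliance. If S is positive, the comparison favours the programme even when E = 0. The documents give no value for S or u.

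**4. If withdrawn patients stay in the analysis.** Assume a gain of 15 percentage points in users and none in non-users. The observed difference is u × 15:
- 0.8 × 15 = 12 points
- 0.6 × 15 = 9 points
- 0.4 × 15 = 6 points

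An observed 6 points fits a 15-point programme used by 40% (0.4 × 15) or a 6-point programme used by everyone (1.0 × 6). No listed variable separates the two.

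Steps 3 and 4 are alternatives. The dilution in step 4 does not apply if the withdrawal rule has removed the non-users.

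**The case against.** The strongest reply is that the main question does not need receipt data. The programme became standard practice in January 2021, and comparing the care offered that year with the care of 2020 is coherent whatever the uptake. This stands. It is why the main comparison should keep every included patient, and it is equally a reason not to withdraw non-compliers from it.

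The reply can add that adherence is watched and that the Limitations section names app adherence. This stands in part. A reader might infer that adherence goes unmonitored, and the control panel shows otherwise. What is missing is a defined, extracted and reported variable. The Limitations section mentions adherence for data collection and, separately, the difficulty of delivering an app-based programme to older people. It proposes support but no measurement.

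Three stronger readings are tempting and not supported:
- A reader might infer that a positive result could not be credited to the exercise rather than to the additional follow-up. The Hypothesis and Study design sections make follow-up part of the exposure, so separating the two is not this study's question.
- A reader might infer that membership rests on calendar year alone. Intended application of the programme, consent and smartphone access also define it.
- A reader might infer that weekly use and level dates are already on file. The documents show only that the physician opens levels and that the panel can reveal poor adherence. The panel might track no more than questionnaire completion.

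**Conclusion.** The point holds. No listed variable records what 2021 patients received, and the non-compliance criterion applies to one cohort, has no measure behind it and conflicts with the whole-cohort analysis.

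Its consequence depends on a choice the documents leave open. If withdrawn patients leave the analysis, the expected bias is (1 − u)·S towards the programme; the direction rests on the assumption that non-compliers would have recovered less well in any case. If they stay, there is no such selection, but a weak result is ambiguous. The 12, 9 and 6 points illustrate that second case only and rest on an assumed 15-point effect and assumed uptake.

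No stated figure is contradicted. Recording uptake would aid interpretation, but it would not remove other differences between 2020 and 2021. This is a worthwhile, low-cost correction, not a reason to regard the design as unusable.

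**What to change.** 1. Reconcile the withdrawal criteria with the Sampling section. For the analysis, make non-compliance a reported flag and not a reason to leave the dataset, with separate flags for the exercise plan and the assessments. Keep all included 2021 patients in the main comparison. This concerns the analysis set only, not clinical decisions about continuing the programme.
2. Add to Tables II and III, for the 2021 cohort, the starting level, the date each level was opened and whatever adherence measure the platform actually holds. Define the exercise-plan flag from that measure.
3. Report uptake beside the between-cohort result.
4. Label any analysis of recovery by uptake as exploratory. Base it on the use measure and not on level reached, because levels open as recovery targets are met and so partly reflect the outcome. Adjust for pre-fracture RNFC and mFAC level, age and Pfeiffer score.

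**Cost:** about one export and one table, if the platform stores the data. Because collection is limited to strictly necessary data, the variables must be named in the protocol, and the consent material may need a matching change. App use is only a proxy for exercise done, may miss the in-hospital phase, and its level of detail is not confirmed by the documents. An analysis by uptake also remains open to confounding by fitness.
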